12.2 Protocol Revisions

After the protocol has been approved by the ethics committee (EC), neither the Principal Investigators nor Study Coordinator Centre staff or Sponsor will modify this protocol without obtaining the concurrence of the others. The Principal Investigator will submit any potential protocol amendments and/or informed consent form modifications to the EC, and approval must be obtained before any amendments are implemented, except when the change(s) involves only logistical or administrative aspects of the study (e.g., typographical errors, inconsistencies).

13-02-2023 This document is confidential. Page 20 of 35

12.3 Record Retention

Data will be maintained for 12 months following the closure of the survey. This DUS will comply with all applicable laws and regulations relating to the privacy of participant's personal information.

12.4 Management and Reporting of Adverse Reactions

Due to the nature of the study, there will be no collection or management of adverse reactions.

12.5 Premature Termination or Suspension of Study

The DUS may be suspended or prematurely terminated if there is sufficient reasonable cause. If the DUS is prematurely terminated or suspended, the Sponsor will promptly inform the appropriate EC and will provide the reason(s) for the termination or suspension. The study may resume once concerns about protocol compliance or data quality are addressed to the satisfaction of the Sponsor and/or the appropriate EC.

12.6 Publication Policy/Disclosure of Data

This study has been requested by a National Competent Authority (i.e., Danish Medicines Agency) during a regulatory procedure. The study report shall be submitted to the requesting National Competent Authority to fulfil the Sponsor's obligation. Scientific publication of the results from this DUS is also foreseen.

13-02-2023 This document is confidential. Page 21 of 35

Appendix 1: Supporting Data for HCP Sample Size Determination

A feasibility assessment was conducted to understand the estimated number of Levosert removals since product launch in each country, the total number of practicing OB-GYNs, and the expected number of OB-GYNs that could be recruited from a large physician panel across the study countries (i.e., OB-GYNs who would be eligible and willing to participate).

The number of Levosert removals in the countries of interest has been estimated from:

- 1. The number of pharmacy-level Levosert sales per country and per year from product launch in 2014 until the last full year of product sales which is 2020 (IMS pharmacy sales database, 2021).
- 2. LNG-IUS user retention after 1 to 5 years of usage as reported by a post-marketing study: 0.94, 0.87, 0.82, 0.76, 0.65, respectively (Backman et al., 2001). For years outside the reported years, 0% retention is assumed resulting in a conservative estimate.

Table 2. Levosert Removals Sin	ce Proc	luct Lau	nch, Es	stimatio	n
Country	2020	2019	2018	2017	- 2

	Country	2020	2019	2018	2017	2016	2015	2014	Total
Czech	Sold	5,803	5,320	5,206	4,233	4,326	2,768	99	27,755
Republic	Removed since (estimated)	348	692	937	1,016	1,514	2,768	99	7,374
	Sold	8,736	11,765	8,971	9,282	8,619	7,931	40	55,344
Poland	Removed since (estimated)	524	1,529	1,615	2,228	3,017	7,931	40	16,884
	Sold	690	907	805	794	907	323	0	4,426
Serbia	Removed since (estimated)	41	118	145	191	317	323	0	1,135
	Sold	1,771	1,824	1,733	1,469	1,485	549	3	8,834
Slovakia	Removed since (estimated)	106	237	312	353	520	549	3	2,080
τ	Jser retention (estimated)	94%1	87%²	82%2	76%²	65%²	0%	0%	

The number of practicing OB-GYNs per country has been estimated based on data from multiple sources (WHO 2021, LKCR 2022, NIL 2021)

Distribution by indications has been estimated based on a multinational LNG-IUS patient survey, which showed that 55% of removals were in patients where IUS was prescribed for heavy menstrual bleeding and the remaining 45% for contraception (Römer et al., 2009).

A summary of Levosert sales and removals from product launch until 2020 in the four study countries, the geographical distribution of OB-GYNs, the expected achievable sample of OB-

-

¹ Based on epidemiological survey of 23,885 LNG-IUS users (Backman et al., 2001).

GYNs in a large physician panel that is active in the study countries, and an estimation of the total number of Levosert removals projected to have been performed by participating Prescribers are shown in Table 3 below:

Table 3. Expected Levosert Removals Performed by Participating Prescribers, Estimation

Item	Czech Republic	Poland	Serbia	Slovakia	Total
Levosert sales since product launch	27,800	55,300	4,400	8,800	96,300
Estimated Levosert removals since product launch	7,400 (27%)	16,900 (31%)	1,100 (25%)	2,100 (24%)	27,500 29%
Total practicing OB-GYNs	2,600	5,900	1,600	1,100	11,200
Estimated Levosert removals per practicing OB-GYN	2.85	2.86	0.69	1.91	2.46
Expected achievable sample of OB-GYNs (from market research panel database)	80	150	100	50	380
Expected Levosert removals performed by participating Prescribers	227	429	69	96	821
Expected Levosert removals performed by participating Prescribers: IUS indicated for HMB (with and without intended contraception) ²	125	236	38	53	452
Expected Levosert removals performed by participating Prescribers: IUS indicated for contraception only (no HMB) ³	102	193	31	43	369

13-02-2023 This document is confidential. Page 24 of 35

² 55% of users reported the aim to shorten/lighten bleeding in a multinational LNG-IUS utilization study (Römer et al. 2009, n=8680)

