8.1.1 Inclusion Criteria

- HCP has its primary practice located in Czech Republic, Poland, Serbia, or Slovakia
- HCP's primary state-certified medical specialty is Gynaecology and Obstetrics.
- HCP spends at least 25% of their professional time in direct patient care, as opposed to teaching, research, or administrative roles
- HCP has prescribed Levosert for HMB to at least two (2) patients
- HCP has removed or replaced Levosert from at least one (1) patient who received the product for HMB

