10.2 Determination of Sample Size

A convenience sampling approach was chosen aiming to reach a sufficiently large group of eligible HCPs who have collectively treated a substantial number of patients with Levosert for the HMB indication.

Based on the size and composition of the physician panel in the four study countries, it is estimated that a sample of approximately 380 HCPs would qualify to complete the questionnaire. Assuming an estimated 27,500 Levosert removals (from product launch until 2020) by approximately 11,200 OB-GYNs across the study countries (average 2.46 Levosert removals per OB-GYN), a sample of approximately 380 HCPs would achieve collective experience with the removal of approximately 820 Levosert IUS. Assuming an approximately balanced distribution by both indications – i.e., contraception only vs. HMB with and without intended contraception: 45% and 55%, respectively (Römer et al., 2009) –, this sample would cover approximately 450 Levosert removals in patients with HMB. Coverage of such a level of collective experience is deemed sufficient to generate a robust estimate on the expected duration of Levosert usage.

See Appendix 1 for detailed data supporting this convenience sampling approach.

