Appendix 2: Screener

S1. In which country is your primary practice located?

1	Poland	POLAND QUOTA=150
2	Czech Republic	CZECH REPUBLIC QUOTA=80
3	Serbia	SERBIA QUOTA=100
4	Slovakia	SLOVAKIA QUOTA=50
98	Other (specify)	TERMINATE

S2. What is your role within your practice?

1	Physician	CONTINUE
2	Nurse	TERMINATE
98	Other (specify)	TERMINATE

S3. What is your primary state-certified medical specialty?

1	General Practice/Internal Medicine	TERMINATE
2	Dermatology	TERMINATE
3	Endocrinology	TERMINATE
4	Gynecology and Obstetrics	CONTINUE
98	Other (specify)	TERMINATE

S4. Approximately what percent of your professional time is spent on direct patient care, as opposed to teaching, research, or administrative roles?

1	Less than 25% of the time	TERMINATE
2	25-50% of the time	CONTINUE
3	51-75% of the time	CONTINUE
4	More than 75% of the time	CONTINUE

S5. How many years have you been practicing Gynecology and Obstetrics since gaining this specialization?

1	0 - 3 years	TERMINATE
2	4 - 10 years	CONTINUE
3	11 - 20 years	CONTINUE
4	More than 20 years	CONTINUE
97	I am not a certified specialist yet	TERMINATE

S6. Which of the following intrauterine systems (IUSs) have you prescribed to your patients? *Please select all that apply.*

1	Levosert (levonorgestrel)	TERMINATE IF NOT SELECTED
2	Mirena (levonorgestrel)	
3	Skyla (levonorgestrel)	
4	Liletta (levonorgestrel)	
98	Other [ANCHOR]	

S7. Which of the following intrauterine systems (IUSs) do you have experience removing (with or without replacement)?

Please select all that apply.

1	Levosert (levonorgestrel)	TERMINATE IF NOT SELECTED
2	Mirena (levonorgestrel)	
3	Skyla (levonorgestrel)	
4	Liletta (levonorgestrel)	
98	Other [ANCHOR]	
97	None [ANCHOR, EXCLUSIVE]	

S8. In the past **10 years**, approximately how many intrauterine systems (IUSs) have you prescribed?

#	TERMINATE IF < 2
π	TEMVIIIVATE II \ Z

S9. Since **Levosert (levonorgestrel)** has been available in your country, for approximately **how many** patients have you prescribed and removed (with or without replacement) Levosert (levonorgestrel)?

	Contraception only	Heavy menstrual bleeding (with and without intended contraception)
Total number of Levosert prescriptions	#	# TERMINATE IF < 2
Total number of Levosert removals (with or without replacement)	#	# TERMINATE IF = 0

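### Table 3 applies a removal average over all OB-GYNs to screened respondents, so 100 Serbian prescribers who must each have at least one HMB removal are given 38

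*Protocol*

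**What the plan says.** - **Eligibility.** Protocol section 8.1.1 requires that "HCP has removed or replaced Levosert from at least one (1) patient who received the product for HMB". Screener item S9 (Appendix 2) enforces this on the HMB removal count: "TERMINATE IF = 0".
- **Who the 380 are.** Section 10.2: "it is estimated that a sample of approximately 380 HCPs would qualify to complete the questionnaire". Appendix 1 describes the recruitable physicians as "OB-GYNs who would be eligible and willing to participate". Table 3 lists them by country in the row "Expected achievable sample of OB-GYNs (from market research panel database": 80 Czech Republic, 150 Poland, 100 Serbia, 50 Slovakia. The screener repeats these numbers as quotas, for example "SERBIA QUOTA=100".
- **What they are expected to have done.** Table 3 gives removals per practising OB-GYN (2.85, 2.86, 0.69 and 1.91; 2.46 overall). It projects 227, 429, 69 and 96 removals, total 821. The HMB row, "Expected Levosert removals performed by participating Prescribers: IUS indicated for HMB (with and without intended contraception", reads 125, 236, 38 and 53, total 452.
- **How the totals are used.** Section 10.2, after citing the 2.46 average, states that "a sample of approximately 380 HCPs would achieve collective experience with the removal of approximately 820 Levosert IUS". It puts about 450 of these in HMB patients and judges that coverage sufficient for a robust estimate of usage duration. The synopsis repeats the figure of about 820.

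**The concern.** A mean over all 11,200 practising OB-GYNs includes those who have never removed a Levosert device. The survey screens those physicians out. Multiplying that mean by the number of screened-in respondents therefore answers a different question from the one the table's row label poses. In Serbia, where the mean is lowest, the mismatch becomes a logical impossibility.

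The totals matter because they are the only basis the protocol offers for calling the sample adequate: there is no hypothesis, power calculation or precision target. The study was committed to a regulator for the HMB indication, and country is a planned subgroup in Table 1, so both the HMB total and the Serbian cell will be read.

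**Working it through.** **Inputs.** From Table 3: removals since launch 7,400 / 16,900 / 1,100 / 2,100 (Czech Republic / Poland / Serbia / Slovakia); practising OB-GYNs 2,600 / 5,900 / 1,600 / 1,100; respondents 80 / 150 / 100 / 50. HMB share 55% (Appendix 1). Minimum HMB removals per respondent: 1 (section 8.1.1, S9).

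**1. Reproduce the plan.** Expected removals = removals ÷ practising OB-GYNs × respondents.

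- Czech Republic: 7,400/2,600 × 80 = 227.7
- Poland: 16,900/5,900 × 150 = 429.7
- Serbia: 1,100/1,600 × 100 = 68.8
- Slovakia: 2,100/1,100 × 50 = 95.5
- Total 821.6; 55% of this is 451.9

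The stated 821 and 452 reproduce within rounding. The multiplication is sound; the fault lies in which mean is multiplied.

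**2. Compare with the eligibility floor** (respondents × 1).

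- Czech Republic: 125 against 80
- Poland: 236 against 150
- Serbia: 38 against 100
- Slovakia: 53 against 50
- Pooled: 452 against 380

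Serbia fails outright at 38/100 = 0.38 HMB removals per respondent. Even its figure for both indications, 69, is below 100.

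**3. Correct the Serbian cell only.** 125 + 236 + 100 + 53 = 514, against 452.

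**4. Condition every country on at least one HMB removal.** With m the mean HMB removals per practising OB-GYN (0.55 × removals ÷ OB-GYNs), the mean among those with at least one is m ÷ P(X ≥ 1). This is never below m, so each cell can only rise. P(X ≥ 1) needs a between-physician distribution, which the protocol does not give. Two assumptions show the range:

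- Poisson: P(X ≥ 1) = 1 − exp(−m)
- Negative binomial, k = 0.5: P(X ≥ 1) = 1 − (k/(k+m))^k

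| | m | Stated HMB | Poisson P(X ≥ 1) | Poisson total | Neg. bin. P(X ≥ 1) | Neg. bin. total |
|---|---|---|---|---|---|---|
| Czech Republic (80) | 1.565 | 125 | 0.791 | 158.3 | 0.508 | 246.5 |
| Poland (150) | 1.575 | 236 | 0.793 | 298.0 | 0.509 | 464.1 |
| Serbia (100) | 0.378 | 38 | 0.315 | 120.1 | 0.245 | 154.1 |
| Slovakia (50) | 1.050 | 53 | 0.650 | 80.8 | 0.432 | 121.5 |
| Total | | 452 | | about 657 | | about 986 |

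The further criterion of at least two HMB prescriptions is not modelled.

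**5. The 2.46 in section 10.2.** 27,500/11,200 = 2.46 is correct. But 380 × 2.46 = 935, not 820. The 821 arises because the sample's country mix differs from that of all OB-GYNs: Serbia, with the lowest rate, supplies 100 of 380 respondents but only 1,600 of 11,200 OB-GYNs. (0.55 × 935 = 514 matches the figure in step 3 by coincidence.)

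**The case against.** **The error is conservative and determines nothing.** The 380 comes from panel availability, and the primary endpoint uses reported removal likelihoods and usage beyond Year 6, not these counts. If 380 eligible prescribers are recruited, their true total is higher than stated, which strengthens the adequacy claim. This stands and limits the weight of the point. It does not make the stated figures right.

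**The pooled totals do not breach the rule.** Correct: 452 exceeds 380, and three of the four countries clear their floors. A reader might infer that 820/450 are themselves impossible; they are not. They are sums that contain one impossible cell, and all their terms use the unconditioned mean.

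**Table 3 stops at 2020, while S9 has no such cut-off and the protocol is dated February 2023.** Rolling Serbia's Table 2 entries forward to end-2022 with the plan's own retention values, and adding no new sales, gives 0.18 × 690 + 0.24 × 907 + 0.35 × 805 + 794 + 907 + 323 ≈ 2,648 removals. That is 1.65 per OB-GYN, or 0.91 for HMB. One hundred average OB-GYNs would then have about 91 HMB removals, still under 100. The protocol makes no such adjustment in any case.

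**A stronger reading: the Serbian quota cannot be filled.** On the 2020 figures, at most 0.55 × 1,100 = 605 of 1,600 Serbian OB-GYNs (38%) could have an HMB removal, implying about 264 screened to find 100. A reader might conclude that too few qualify. The documents do not support this. Even 605 is about six times the quota; the end-2022 roll-forward lowers the screening minimum to about 110 (100/0.91); panel size is not given; and Appendix 1 describes the 100 as already eligible and willing. There is no basis here for saying that the quota is unattainable or should be lowered.

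**Section 10.2 merely compresses Appendix 1.** It does refer the reader there, and the country rates do give 821. The sentence still names an input that does not produce its output.

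**Conclusion.** Wrong as written, with modest consequences. The Serbian contradiction (38 stated, minimum 100) is exact and needs no assumption beyond the protocol's own eligibility rule and quota. The planning figures of 820 and 450 do not describe an eligible sample.

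That they understate its experience assumes that the quotas fill, that the plan's country means hold, and that eligible respondents resemble eligible OB-GYNs generally. On those terms the HMB total is at least 514. The figures of about 657 and 986 are illustrations that depend on the assumed spread between physicians; neither is a replacement estimate on its own. The 2.46 in section 10.2 is a separate, smaller error of presentation. Nothing here shows that the study would collect too little experience.

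**What to change.** 1. Recompute Table 3 conditional on at least one HMB removal per respondent, stating the distribution assumed and giving a range. Alternatively, keep the present figures but label 820/450 as unconditional lower-end estimates based on removals to 2020, and note that the Serbian cell lies below the minimum that eligibility guarantees.
2. Bring the synopsis (820) and section 10.2 (820 and 450) into line with whichever is chosen.
3. In section 10.2, cite the country-specific rates of Table 3 in place of the 2.46 average.

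The cost is a short recalculation and text changes in three places. No quota, eligibility criterion, questionnaire item or analysis needs to change.

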Appendix 2: Screener

S1. In which country is your primary practice located?

1	Poland	POLAND QUOTA=150
2	Czech Republic	CZECH REPUBLIC QUOTA=80
3	Serbia	SERBIA QUOTA=100
4	Slovakia	SLOVAKIA QUOTA=50
98	Other (specify)	TERMINATE

S2. What is your role within your practice?

1	Physician	CONTINUE
2	Nurse	TERMINATE
98	Other (specify)	TERMINATE

S3. What is your primary state-certified medical specialty?

1	General Practice/Internal Medicine	TERMINATE
2	Dermatology	TERMINATE
3	Endocrinology	TERMINATE
4	Gynecology and Obstetrics	CONTINUE
98	Other (specify)	TERMINATE

S4. Approximately what percent of your professional time is spent on direct patient care, as opposed to teaching, research, or administrative roles?

1	Less than 25% of the time	TERMINATE
2	25-50% of the time	CONTINUE
3	51-75% of the time	CONTINUE
4	More than 75% of the time	CONTINUE

S5. How many years have you been practicing Gynecology and Obstetrics since gaining this specialization?

1	0 - 3 years	TERMINATE
2	4 - 10 years	CONTINUE
3	11 - 20 years	CONTINUE
4	More than 20 years	CONTINUE
97	I am not a certified specialist yet	TERMINATE

S6. Which of the following intrauterine systems (IUSs) have you prescribed to your patients? *Please select all that apply.*

1	Levosert (levonorgestrel)	TERMINATE IF NOT SELECTED
2	Mirena (levonorgestrel)	
3	Skyla (levonorgestrel)	
4	Liletta (levonorgestrel)	
98	Other [ANCHOR]	

S7. Which of the following intrauterine systems (IUSs) do you have experience removing (with or without replacement)?

Please select all that apply.

1	Levosert (levonorgestrel)	TERMINATE IF NOT SELECTED
2	Mirena (levonorgestrel)	
3	Skyla (levonorgestrel)	
4	Liletta (levonorgestrel)	
98	Other [ANCHOR]	
97	None [ANCHOR, EXCLUSIVE]	

S8. In the past **10 years**, approximately how many intrauterine systems (IUSs) have you prescribed?

#	TERMINATE IF < 2
π	TEMVIIIVATE II \ Z

S9. Since **Levosert (levonorgestrel)** has been available in your country, for approximately **how many** patients have you prescribed and removed (with or without replacement) Levosert (levonorgestrel)?

	Contraception only	Heavy menstrual bleeding (with and without intended contraception)
Total number of Levosert prescriptions	#	# TERMINATE IF < 2
Total number of Levosert removals (with or without replacement)	#	# TERMINATE IF = 0

S10. Are you, or any member of your household, affiliated with or employed by any pharmaceutical companies as a consultant and/or researcher **other than participating in clinical studies or clinical investigations**?

1	Yes	TERMINATE
2	No	

Thank you. You qualify to participate in this research. When you click "Next" you will be taken to a questionnaire which should take about **10 minutes** to complete.

Please answer as completely and as accurately as you can. There are no wrong answers; we are only interested in your experience with and expert opinion on contraceptive products.

The questionnaire is to be completed now and at one sitting. However, if for any reason you are interrupted (e.g., connection failure), you will be able to restart the questionnaire where you left it by clicking back onto your invitation message link.

Let's proceed...

Appendix 3: HCP Questionnaire

Q1. In a typical month without COVID-19 restrictions, approximately how many patients do you personally manage?

Please consider patients seen both in-person or via virtual/online visit.

Please exclude any patients only seeking prescription refills.

# of total patients / month	

- **Q2.** Approximately, how many of your patients are **currently using** one of the following types of contraception by indication?
 - ✓ Oral/pill
 - ✓ Intrauterine device (IUD)
 - ✓ Intrauterine system (IUS)
 - ✓ Hormonal ring
 - ✓ Implant
 - ✓ Injection

	Contraception only	Heavy menstrual bleeding (with and without intended contraception)
# of patients currently using any of the above treatment types	#	#

Q3. Considering **all your patients by indication,** approximately what percentage are currently using the different types of contraception listed below?

	Contraception only	Heavy menstrual bleeding (with and without intended contraception)
Oral/pill	%	%
Intrauterine device (IUD)	%	%
Intrauterine system (IUS)	%	%
Hormonal ring	%	%
Implant	%	%
Injection	%	%
Total	100%	100%

Q4. Considering all your patients currently using intrauterine systems (IUSs) by indication, approximately what percentage are using Levosert (levonorgestrel)?

	Contraception only	Heavy menstrual bleeding (with and without intended contraception)
Proportion of patients currently using IUSs who receive Levosert	%	%

Q5. Considering **all** your patients ever having used and/or currently using **Levosert (levonorgestrel)**, what is the age distribution at the time of prescription, by indication?

	Contraception only	Heavy menstrual bleeding (with and without intended contraception)
16-24 years of age	%	%
25-34 years of age	%	%
35-44 years of age	%	%
45-54 years of age	%	%
55+ years of age	%	%
Total	100%	100%

Q6. When using **Levosert (levonorgestrel)** for **heavy menstrual bleeding (with and without intended contraception)**, what is the average time from insertion to achieving treatment effectiveness (defined as significant reduction in menstrual blood loss)?

1	Less than one month	
2	One to less than two months	
3	Two to less than three months	
4	Three to less than four months	
5	Four months or more	

Q7. In your experience, approximately what percentage of patients using **Levosert (levonorgestrel)** for the following indications need to get it **removed (with or without replacement)** by the end of each year (cumulatively since insertion)?

Please note your responses must be cumulative over time (since insertion).

	Contraception only	Heavy menstrual bleeding (with and without intended contraception)
By the end of Year 1	%	%
By the end of Year 2	%	%
By the end of Year 3	%	%
By the end of Year 4	%	%
By the end of Year 5	%	%
By the end of Year 6	%	%

VALIDATION MESSAGE REQUIRING TRANSLATION:

ERROR: Please note your responses for each column must be cumulative. For example, your response for the end of year 2 must be equal to or greater than your response for the end of year 1, etc.

Q8. For patients who use **Levosert (levonorgestrel)** for **contraception only** for more than six years, for approximately how many years in total do these patients typically use **Levosert (levonorgestrel)**?

Please feel free to provide a fractional number of years.

	# of years	RANGE 7-10
--	------------	------------

Q9. For patients who use **Levosert** (**levonorgestrel**) for **heavy menstrual bleeding** (with and without **intended contraception**) for more than six years, for approximately how many years in total do these patients typically use **Levosert** (**levonorgestrel**)?

Please feel free to provide a fractional number of years.

	# of years	RANGE 7-10
--	------------	------------

13-02-2023

Q10. Among your patients using Levosert (levonorgestrel) for heavy menstrual bleeding (with and without intended contraception), what percentage would continue to show treatment effectiveness by the end of each year (cumulatively since insertion), while continuing to use the same Levosert (levonorgestrel) device.

Please note your responses must be cumulative over time since insertion.

Treatment effectiveness is defined as significant reduction in menstrual blood loss.

		Heavy menstrual bleeding (with and without intended contraception)
1	By the end of Year 1	%
2	By the end of Year 2	%
3	By the end of Year 3	%
4	By the end of Year 4	%
5	By the end of Year 5	%
6	By the end of Year 6	%
7	Beyond 6 years	%

VALIDATION MESSAGE REQUIRING TRANSLATION:

ERROR: Please note your responses for each column must be cumulative. For example, your response for the end of year 2 must be equal to or less than your response for the end of year 1, etc.

Q11. Considering **all** your patients ever having used and/or currently using **Levosert (levonorgestrel)** for the following indications and who had it removed (with or without replacement), approximately what percentage of these patients had **Levosert (levonorgestrel)** removed for each of the following reasons?

	Contraception only	Heavy menstrual bleeding (with and without intended contraception)
Removed per Schedule (IUS Expiry)	%	%
Planning for family	%	%
Side effects	%	%
Lack of effectiveness	%	%
Menopausal	%	%
Other (specify)	%	%
Total	100%	100%

Q12. Overall, how satisfied are you with **Levosert (levonorgestrel)** in patients who use it **for three or more years** for the following indications?

	Contraception only	Heavy menstrual bleeding (with and without intended contraception)
Not at all satisfied	1	1
Not very satisfied	2	2
Somewhat satisfied	3	3
Very satisfied	4	4
Do not have enough experience to rate	99	99

Q13. What is the recommended duration of use of Levosert (levonorgestrel) for heavy menstrual bleeding (with and without intended contraception) in your country?

1	3 years	
2	4 years	
3	5 years	
4	6 years	
99	Do not know	

In closing, we would like to ask you a few last questions about your practice	
---	--

Q14. Please enter the postal code of the practice setting where you spend the majority of your time?

Q15. Which of the following best describe the practice setting where you spend the majority of your time?

1	Hospital-based/inpatient practice	
2	Multi-specialty outpatient practice, including OB/GYN specialty	
3	Single specialty outpatient OB/GYN practice	
98	Other	

Thank you for your time! Please read this and make sure to click the arrow button below to submit your survey.

If you are aware of individual adverse reactions with **Levosert (levonorgestrel)** that were not reported previously, please kindly report them to the national reporting system of your practice location or the drug safety contact of the Sponsor!

Contact details of the national reporting system and the Sponsor for your primary practice location:

Poland	National Reporting System
	Departament Monitorowania Niepożądanych Działań Produktów Leczniczych Urzędu Rejestracji Produktów Leczniczych, Wyrobów Medycznych i Produktów Biobójczych
	[name]
	[name]
	Tel.: [name]
	Faks: [name]
	https://smz.ezdrowie.gov.pl
	Sponsor Drug Safety Contact
	Gedeon Richter Polska Sp. z o.o.
	E-mail: [contact]
	[contact]
	https://www.gedeonrichter.pl/zgloszenie-dzialania-niepozadanego/
Czech Republic	National Reporting System
	Státní ústav pro kontrolu léčiv
	[name]
	[name]
	http://www.sukl.cz/nahlasit-nezadouci-ucinek
	Sponsor Drug Safety Contact
	Gedeon Richter Marketing ČR, s.r.o.
	[name]
	[name]
	E-mail: [contact]
	[contact]
	https://www.richtergedeon.cz/hlaseni-nezadoucich-ucinku/
Serbia	National Reporting System
	Medicines and Medical Devices Agency of Serbia

13-02-2023 This document is confidential.

